5.2 Recruitment Methods

Up to 750 participants across all sites (including partner telehealth sites) will be recruited and enrolled in the project. The study has an overall final enrollment goal of 472. Table 1 below outlines expected enrollment by site and year.

	Year 1				Year 2				Year 3				Year 4					
Site	Q 1	Q 2	Q 3	Q 4	Q 1	Q 2	Q 3	Q 4	Q 1	Q 2	Q 3	Q 4	Q 1	Q 2	Q 3	Q 4	Enroll	Retention
Seattle			2 groups			4 groups				4 groups			2 groups				96	72
Cleveland			2 groups			4 groups				4 groups			2 groups				96	72
Houston			2 groups			5 groups				5 groups			3 groups				120	90
Tampa			2 groups			4 groups				4 groups			2 groups				96	72
Minneapolis			N/A			4 groups				4 groups			TBD				64	48
Total	E = 64		C = 48		E = 168		C = 126		E = 168		C = 126		E = 72		C = 54		472	354

Table 1: Projections assume group enrollment rate (E) of N=8±2 and completion rate (C) of N=6 per group. Based upon a 50% enrollment rate. Based upon a 75% follow-up retention rate.

The recruitment methods employed throughout the study ensure that the study sites can capture 100% of the patient population that meets inclusion and exclusion criteria. The recruitment plan ensures that we will be able to successfully identify patients in this specialized population, and that the only excluded patients are those that are clinically ineligible for this study.

Patient identification and Pre-screening

VA patients who recently had an amputation or are scheduled for an amputation are identified on an ongoing basis using computerized clinic lists from CPRS. Study coordinators may also receive alerts from ICD-9 codes and hospital admissions to identify VA patients. Alerts are created by CPRS programmers at each study site. The study coordinator screens the medical record to identify potentially eligible participants and determine if the patient has an upcoming clinic appointment for amputee-related post-operative care. The study coordinator attends clinic appointments and asks providers to determine if the patient might be eligible and interested. Providers approach patients who may be eligible and interested in the study, and ask if the patients would agree to be contacted by the study coordinator. If the patient agrees, the study coordinator initiates contact following the clinic appointment, either in person or by telephone.

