For hypotheses 1a and 1b, we will use Generalized Estimating Equations (GEE) linear regression to investigate mean change over time in MFA-SF. We will model the mean MFA-SF change over time as the outcome, using contrasts $D = MFA-SF[Post\ Intervention] - MFA-SF[baseline]$ and $D = MFA-SF[6\ months] - MFA-SF[baseline]$, versus a treatment indicator, T. The treatment indicator assigns patients T=1 if they receive the VETPALS intervention and T=0 if they receive enhanced usual care. The GEE model will account for intra-cohort level correlation among patients' measurements. The GEE model will provide valid statistical inference if the correlation or variance structure is mis-specified. It does not require normality of model errors. Since the focus of the investigation is to estimate within-patient changes (over time) and the outcome are intra-patient level differences, repeated measures correlation is appropriately accounted for in the model variance estimates. Similarly, we will model the mean PHQ-9 change over time as the outcome, using contrasts $D = PHQ-9[Post\ Intervention] - PHQ-9[baseline]$ and $D = PHQ-9[6\ months] - PHQ-9[baseline]$, versus a treatment indicator, T. The primary analysis will be an as-randomized efficacy assessment comparing the self-management intervention and individual education groups for improvements in depression and physical functioning. The follow-up assessments of participants who do not complete all self-management sessions in the intervention condition will still be included with those who complete the expected course of treatment. This type of analysis provides a more conservative and ecologically valid estimation of treatment effect because it retains all participants and does not screen out individuals who do not tolerate the intervention. Effect size estimates will be obtained. We will assess the randomization assignment by comparing patient-level characteristics (e.g., age, gender, and amputation level) by the treatment indicator and adjust our models with appropriate covariates as necessary.

For hypotheses 2a-e, similar to above, we will fit a GEE model to investigate differences in mean changes in each outcome variable (VAR). We will model the mean change over time as the outcome, using contrasts $\Delta = VAR[Post\ Intervention] - VAR[baseline]$ and $\Delta = VAR[6\ months] - VAR[baseline]$, versus a treatment indicator, T. The treatment indicator assigns patients T=1 if

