Retention: The original PALS self-management study maintained a greater than 90% retention rate. Even assuming a more conservative 75% retention rate for the proposed study, 118 participants per year would be expected to participate and successfully reach their final follow-up. Over the course of 3 years, we expect to retain 354 enrollees. In sum, our sample size estimates are grounded in the specific experience of our team enrolling actual Veterans with limb loss at VA facilities and reflect conservative estimates of recruitment and retention. This is done out of an abundance of caution and we expect that actual rates of recruitment and retention are likely to be higher.

Each primary site intends to recruit one additional secondary site to partner with each primary site (e.g. Seattle partners with Tucson VA). Enrollment, retention, and power analysis sections do not reflect these anticipated partners and do not require them. The purpose of including additional sites is to extend the recruitment and generalizability of the project aims to integrate VETPALS into the VA Amputation System of Care.

Statistical Power

Power estimates are based upon the sample size projections provided in Table 1 below (also in 5.2 Recruitment Methods). Effect size estimates were obtained using the estimates provided in the original PALS study. We anticipated an enrollment of N=51 cohorts in total for the study and

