between 6-10 patients per cohort. The treatments, VETPALS and individual education, will be evenly and randomly assigned by cohort. We project between 300 to 500 total patients participating in this study. We investigated changes in each outcome by first computing intra-patient change and accounting for possible intra-cohort level correlation. We assume the baseline and six-month values for the outcomes are highly correlated, with Pearson correlation between 0.6 and 0.8, and the correlation among the change values within a cohort to be modestly correlated, with an intra-class correlation between 0.01 and 0.10. To estimate statistical power to detect the anticipated effect sizes at these proposed sample sizes and correlations, we conducted a series of Monte Carlo simulations based on the analytic framework outlined above. Each of the power calculations were based on 1,000 simulated datasets. Power was computed empirically as the proportion of Wald tests (from correlated data regression estimates from the simulated datasets) that correctly rejected the null hypothesis of no effect, at a five percent alpha level (Type I error rate).

The results indicate that for the modest effect sizes provided, low levels of intra-cohort correlation (ICC) and modest Pearson correlation levels between baseline and six-month measurements (ρ), we will have adequate power to detect differences between the study conditions. To provide two examples, given these conditions we will have power of greater than .8 to detect differences in the primary outcome physical functioning (MFA-SF) (and the additional outcome self-efficacy (MSES).

Anticipated Enrollment

Table 1 (page 25) indicates anticipated enrollment across all 5 sites throughout the 4-year study period. Projections assume a group enrollment rate of 8 ± 2 participants and completion rate of 6 participants per group. We estimate a 50% enrollment rate and expect a 75% retention rate.

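### The plan calls GEE inference valid without allowing for only 51 to 59 cohorts and names no small-sample correction; the standard test would modestly exceed its 5% error rate

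*Combined protocol and SAP*

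**What the plan says.** Section 5.6, under the heading on the primary aims, regresses each patient's change from baseline on a treatment indicator by linear GEE. On clustering it says: "The GEE model will account for intra-cohort level correlation among patients' measurements". On validity it says: "The GEE model will provide valid statistical inference if the correlation or variance structure is mis-specified". The same approach is used for hypotheses 2a-e. Hypothesis 2f is handled by Pearson correlations.

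Under Statistical Power the cohort count is given: "We anticipated an enrollment of N=51 cohorts in total for the study". The test appears only in the account of the power simulation: "Power was computed empirically as the proportion of Wald tests", carried out "at a five percent alpha level (Type I error rate"). No separate significance level is set for the analysis itself.

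Table 1 in section 5.2 implies a different count. Its groups sum to 12 + 12 + 15 + 12 + 8 = 59, and 59 × 8 = 472, the stated enrollment goal. Leaving out Minneapolis gives 51.

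Models are to be adjusted for covariates where needed. The examples in section 5.6 (age, gender, amputation level) and the potential covariates in section 5.5 are patient-level. Section 5.1 balances groups by site in the randomization, but site is not named as a model term. Neither section 5.6 nor any other gives a small-sample variance correction, a t reference or degrees of freedom.

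**The concern.** GEE inference survives a wrong working correlation because of the empirical (sandwich) variance. That estimator is biased downward when clusters are few, and the independent units here are cohorts, not patients. A normal reference adds to the problem by ignoring the uncertainty in the variance estimate. Both effects make standard errors and p-values too small, so the error runs in one direction, toward false positives.

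Treatment is assigned by cohort, so each further cohort-level term in the model uses up information from the same 51 to 59 units and makes the bias worse. If the power simulation used the same uncorrected test, its power figures are slightly optimistic for the same reason.

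**Working it through.** **Inputs from the plan.** K = 51 cohorts (5.6) or 59 (Table 1); 8 ± 2 enrolled and 6 completing per cohort (Table 1); 1:1 allocation by cohort; intra-cohort correlation (ICC) of change scores 0.01 to 0.10; nominal error 5%.

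**Assumptions.** Two-sided test, normal errors, exchangeable working correlation, cohort sizes spread evenly over 6-10 or 4-8, and the standard sandwich variance with a normal reference, since the plan names no alternative.

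**1. The plan's own figure.** The stated 5% is a nominal level. No simulated rejection rate under the null is reported, so there is nothing to reproduce directly. The question is what a nominal 5% delivers.

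**2. Closed form, equal cohorts.** With p cohort-level parameters, the uncorrected variance averages about (K − p)/K of the unbiased one. The true error is then P(|t with K − p df| > 1.96 × √((K − p)/K)).

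| K | Model | p | Cut-off on the t scale | True error |
|---|---|---|---|---|
| 51 | treatment only | 2 | 1.96 × √(49/51) = 1.921 | 6.05% |
| 59 | treatment only | 2 | 1.96 × √(57/59) = 1.926 | 5.90% |
| 51 | plus five sites | 6 | 1.96 × √(45/51) = 1.841 | 7.2% |
| 59 | plus five sites | 6 | 1.96 × √(53/59) = 1.858 | 6.9% |

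The correct 97.5% t points are 2.010 and 2.003 (treatment only) and 2.014 and 2.006 (with sites). The uncorrected 95% interval is therefore about 4% too narrow with treatment only (1.921/2.010 = 0.956; 1.926/2.003 = 0.962). With sites it is 7 to 9% too narrow (1.841/2.014 = 0.914; 1.858/2.006 = 0.926).

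**3. Simulation under the null.** There were 10,000 to 12,000 replicates per case (Monte Carlo standard error about 0.2 points), with ICC 0.01, 0.05, 0.10, or 0 in control and 0.10 in intervention.

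| Model | K = 51 | K = 59 |
|---|---|---|
| Treatment only | 6.1-6.5% | 5.8-6.3% |
| Plus three patient-level covariates | 6.2-6.7% | 6.0-6.3% |
| Plus site (four or five sites at K = 51, five at K = 59) | 6.6-7.5% | 6.6-7.2% |

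Separately programmed runs of the same test gave rates down to 5.5% with treatment only and 6.9 to 7.4% with five sites. Patient-level covariates add almost nothing; cohort-level ones do.

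**4. Possible corrections.**
- Kauermann-Carroll variance with t on K − p df: 4.6 to 5.5% in all 51- and 59-cohort cases.
- t reference alone, variance uncorrected: 5.3 to 6.1% without cohort-level covariates and 5.9 to 7.5% with them, so not enough.
- Mancl-DeRouen variance with t: 4.2 to 5.0% without cohort-level covariates and 3.6 to 4.1% with site, so it over-corrects once site is in the model.

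**5. Power.** The plan's claim of power above 0.8 cannot be reproduced, because no effect size or standard deviation is given. Instead, take a difference sized for a nominal 80% at ICC 0.05 and 8 per cohort: (1.960 + 0.842) × √(2 × 1.35/(4K)) = 0.322 (K = 51) or 0.300 (K = 59) standard deviations of change, where 1.35 = 1 + 7 × 0.05. Moving from the uncorrected z test to Kauermann-Carroll with t (5,000 replicates) gives:

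| K | Treatment only | With site |
|---|---|---|
| 51 | 80.6% to 78.1% | 81.1% to 76.8% |
| 59 | 81.1% to 79.6% | 82.5% to 78.5% |

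**The case against.** **The plan never says that the test is uncorrected.** True. It does not use the word sandwich, and a Wald test can carry a corrected variance or a t reference. The inflation is conditional on the standard choice. What stands is that the plan asserts validity without qualification and leaves the variance estimator open, so an analyst following it could use the uncorrected test.

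**The validity sentence is correct in itself.** As a large-sample statement about a mis-specified working correlation, it is. What is missing is the limit set by the number of cohorts.

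**Stronger readings a reader might infer.**
- *The error rate of the planned analysis is 7% or more.* That needs a cohort-level term. Site is a foreseeable one, because groups are balanced by site, but the plan does not name it, and the covariates that it does name are patient-level.
- *The projection of 300 to 500 patients implies about 40 cohorts.* At that count with five sites the error would be about 8%. But 51 × 6 = 306 and 51 × 10 = 510, so the projected range reflects cohort size at a fixed 51 cohorts.
- *Every primary and secondary test is affected.* Hypothesis 2f uses Pearson correlations, not GEE.
- *The trial is underpowered.* The plan claims only that power exceeds 0.8 and gives no effect size, so a shortfall cannot be shown.

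**The excess is small.** Also fair: for the planned model it is about 0.5 to 1.5 points.

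**Conclusion.** The point holds in a limited form. The validity claim lacks a small-sample qualification, and the plan does not say how the variance or the reference distribution will be chosen. With the standard sandwich z test and 51 or 59 cohorts, the true error at a nominal 5% is about 5.5 to 6.5% for the planned model. It would be roughly 7 to 7.5% if site were added. The GEE tests and intervals for hypotheses 1a-b and 2a-e are affected.

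The conclusion is the same for either cohort count and across the plan's ICC range. It rests on a two-sided test, normal errors, near-balanced allocation and, above all, the assumption that no correction would be applied. It is a cheap improvement, modest in size, and does not threaten the design.

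**What to change.** Add a sentence to section 5.6: all GEE tests and confidence intervals use a Kauermann-Carroll bias-corrected sandwich variance with a t reference on the number of cohorts minus the number of cohort-level parameters. Name this one estimator, because Mancl-DeRouen with t is not interchangeable with it here. State whether site enters the model. Recompute the stated power with the same test and report the simulated rejection rate under the null beside it.

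The cost is a software option, slightly wider intervals and a rerun of the power simulation, which needs effect sizes that the document does not report. Power falls by about 1.5 to 2.5 points at a nominal 80% without site and about 4 points with it; part of the power given up came from the inflated error rate. Recruitment, data collection and participants are unaffected.

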5.6 Data Analysis

Data analysis will be performed by the study biostatistician ([name]) and consultant ([name]) with input from investigator-level study staff (Drs. [name], [name], [name], site PIs). Data analysis will occur at Spectrum Research, Inc. (Tacoma, WA), the University of Washington (Seattle, WA), and Oregon Health & Science University (Portland, OR). Data that is off-site at Spectrum Research, University of Washington, and OHSU for analysis will be coded and will not contain any HIPAA identifiers. See 7.0 *Privacy and Confidentiality* for additional details on data analysis and storage at these locations.

Descriptive Statistics

We will produce descriptive statistics for the recruitment and retention of participants, as well as the frequency of session participation in the intervention group. We will also produce descriptive statistics of patient demographic characteristics, covariates, and outcome measures. For categorical variables, proportions and frequency counts will be calculated. For continuous variables, means, standard deviations, medians, minimum and maximum will be computed. Missing, extreme, and variable distributions will be explored. Missing values patterns will be analyzed.

Statistical analysis of the primary aims

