they receive VETPALS and T=0 if they receive individual education support. The primary analysis will again be a randomized efficacy assessment comparing the self-management intervention and control groups for improvements in self-efficacy, patient activation, and problem solving. The follow-up assessments of participants who do not complete all self-management sessions in the intervention condition will still be included with those who complete the expected course of treatment. This type of analysis provides a more conservative and ecologically valid estimation of treatment effect because it retains all participants and does not screen out individuals who do not tolerate the intervention. Primary analyses will examine changes between baseline and 6-month follow-up scores on outcome measures by treatment group, but we will also examine changes in outcome immediately following the intervention. Effect size estimates will be obtained. Models will be adjusted for covariates as necessary.

For hypothesis 2f, we will produce mean change scores, $\Delta = VAR[6\ months] - VAR[baseline]$, for each outcome measure. We will utilize Pearson product moment correlations to establish associations between changes in our intermediate outcomes and changes in our primary outcomes. This series of analyses is both secondary and exploratory, and is intended to produce preliminary data for a future explanatory model hypothesizing that improvements in self-efficacy, patient activation, and problem solving represent causal mechanisms of self-management intervention that in turn produce improvements in physical and psychosocial outcomes.

Sample Size Justification

Enrollment: Between our 5 sites, we anticipate enrolling approximately 157 subjects per year of recruitment based on previous numbers from the National VA Registry and our already established record of enrollment and follow-up in previous amputation studies conducted by the same core group of investigators. This is a conservative estimate as the inclusion/exclusion criteria for this proposal are more lenient than in our previous studies examining individuals with their first, unilateral amputation. Nonetheless we cautiously project enrollment at 55% of 286, or 157 participants per year. Over the course of 3 years, we expect to accrue 472 enrollees.

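### The 6-month change-score GEE keeps only participants who have a 6-month value (75% at the planned rate), no missing-data method is named, and the estimate can be biased if outcome-related loss acts differently by arm

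*Combined protocol and SAP*

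**What the plan says.** Section 5.6 (Statistical analysis of the primary aims) takes the change score as the outcome: "We will model the mean MFA-SF change over time as the outcome, using contrasts" of post-intervention minus baseline and 6 months minus baseline. The regressor is the treatment indicator, and covariates are added as necessary. PHQ-9 and the outcomes of hypotheses 2a-e are handled the same way. The text does not say whether the two contrasts are fitted separately or stacked. Six months is named as the main time point only in the paragraph on hypotheses 2a-e: "Primary analyses will examine changes between baseline and 6-month follow-up scores on outcome measures by treatment group".

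The analysis is by randomized group. The plan states that "The follow-up assessments of participants who do not complete all self-management sessions in the intervention condition will still be included" and then calls the estimate conservative because "it retains all participants and does not screen out individuals who do not tolerate the intervention".

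On numbers, section 5.2 says "The study has an overall final enrollment goal of 472", and the note to Table 1 adds "Based upon a 75% follow-up retention rate". The Retention paragraph of 5.6 repeats this ("Even assuming a more conservative 75% retention rate for the proposed study") and arrives at 354 reaching final follow-up. On missing data, the only relevant sentence is under Descriptive Statistics: "Missing values patterns will be analyzed".

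**The concern.** A change score does not exist without the follow-up value. Anyone lost before 6 months leaves the 6-month contrast, and nothing in the plan brings back the information in their baseline and 6-week scores. The sentence about retaining everyone hides this, and it may explain why no missing-data method was written.

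At stake is the effect estimate for both primary outcomes. If those who leave differ in their course from those who stay, and this happens differently in the two arms, the completers no longer give the randomized comparison. The error can go either way, so the plan's description of the estimate as conservative is not assured.

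Arm-dependent loss is plausible. VETPALS takes 4 + 4 × 2 = 12 hours of group classes, while control consists of education materials and individual contact. Section 5.7 also lets investigators suspend a participant who disrupts the intervention group, a route with no counterpart in control, although it does not say that outcome assessment then stops.

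**Working it through.** **1. Reproducing the plan's figures.** 472 × 0.75 = 354. Table 1 implies 59 groups: 59 × 8 = 472 enrolled and 59 × 6 = 354 retained. Per year, 157 × 0.75 = 117.75, rounded to 118. All agree with the documents.

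**2. Participants outside the 6-month contrast.** 472 - 354 = 118, and 118/472 = 25.0%. Loss at 6 weeks is not stated.

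**3. When this causes bias.** In one arm let p be the proportion lost and d the mean change of completers minus that of dropouts. The arm mean is (1 - p) × completers + p × dropouts, so the completer mean exceeds the arm mean by p × d. The bias in the treatment difference is p1·d1 - p0·d0. With d in SD of change (the documents give neither p by arm nor d, so these are assumptions):

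- 35% vs 15%, d = 0 in both arms: 0
- 25% vs 25%, d = 0.5 in both: 0.125 - 0.125 = 0
- 30% vs 20%, d = 0.5 in both: 0.15 - 0.10 = 0.05
- 35% vs 15%, d = 0.5 in both: 0.175 - 0.075 = 0.10
- 25% vs 25%, d = 0.5 in one arm and 0 in the other: 0.125

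Unequal rates are therefore neither sufficient (first line) nor necessary (last line) for bias.

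**4. Yardstick.** Section 5.6 (Statistical Power) gives no effect size, so its power figure cannot be reproduced. A detectable difference can be computed with 354 completers, 6 per cohort, ICC 0.01 to 0.10, 80% power and alpha 0.05, taken as two-sided (an assumption). The design effect is 1 + 5 × ICC = 1.05 to 1.50. The effective n per arm is 177/1.05 = 168.6 to 177/1.50 = 118. The detectable difference is (1.960 + 0.842) × √(2/n) = 0.305 to 0.365 SD of change. With equal variances at both times, the SD of change is √(2(1 - ρ)) baseline SD, that is 0.894 at ρ = 0.6 and 0.632 at ρ = 0.8. In baseline SD the detectable difference is 0.27 to 0.33 (ρ = 0.6) or 0.19 to 0.23 (ρ = 0.8).

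**5. Illustrative bias in baseline SD.** Large-sample simulation with true effect 0, ρ from the plan, and an assumed correlation of (1 + ρ)/2 between adjacent visits. Loss is logistic, with the slope given per SD of the driver. The driver is baseline severity (first figure) or early worsening from baseline to 6 weeks (second figure). A positive value makes VETPALS look worse on a scale where higher is worse, as with the PHQ-9.

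| Loss, VETPALS / control | Mechanism | ρ = 0.6 | ρ = 0.8 |
|---|---|---|---|
| 35% / 15% | unrelated to scores | 0.00 | 0.00 |
| 25% / 25% | slope 1, both arms | 0.00, 0.00 | 0.00, 0.00 |
| 30% / 20% | slope 0.5, both arms | +0.02, -0.03 | +0.01, -0.02 |
| 30% / 20% | slope 1, both arms | +0.03, -0.05 | +0.02, -0.04 |
| 25% / 25% | slope 1, VETPALS only | +0.09, -0.13 | +0.04, -0.10 |
| 30% / 20% | slope 1, VETPALS only | +0.10, -0.16 | +0.05, -0.11 |

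With the same mechanism in both arms, the largest share of the detectable difference is about one fifth (0.05/0.27 = 0.19; 0.04/0.19 = 0.21). With a strong mechanism in one arm only it reaches about three fifths (0.16/0.27 = 0.59; 0.11/0.19 = 0.58).

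A regression on baseline and 6-week scores within arm removed the bias in every row. It does so by construction, because loss was generated from those scores. For loss driven by baseline alone, adding baseline as a covariate was already enough.

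**The case against.** The sentence about retaining participants follows one on session non-completers and sets the analysis apart from a per-protocol one. In that sense it is correct. A reader might infer that the as-randomized claim is false. It is not: participants are grouped by assignment, and missing outcomes do not undo that.

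A reader might also infer from the 12-hour course that dropout from assessment will differ by arm. No figure in the documents shows this. Outcomes are collected outside the classes by blinded coordinators, in person or by phone, in up to 30 minutes at follow-up, with $20 per visit in both arms (sections 5.1, 5.2 and 5.5). In the original PALS trial only 64.7% of the intervention arm met the attendance threshold (Limitations of the initial PALS trial), yet study retention exceeded 90% (section 5.6). Attendance and outcome retention are different quantities. The 25% is a deliberately cautious planning value, and the plan expects better.

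The larger biases need a slope of 1 per SD, an odds ratio of about 2.7, in one arm and none in the other. The 6-week score cannot help for people lost before week 6. Some of the missing will have died, and imputing their scores would be wrong.

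All of this stands, and it limits the size and certainty of the concern. It does not supply a missing-data method, and it does not make the retention sentence true of people without a 6-month assessment. Stacking the two contrasts would not settle it either: the plan names neither weights nor imputation, and an unweighted GEE does not in general protect against loss that depends on earlier outcomes.

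**Conclusion.** The point holds in limited form and is worth correcting before analysis. At the planned retention, 118 of 472 participants (25%) cannot enter the 6-month contrast, and the retention sentence is true only for session non-completers who are still assessed.

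Bias requires loss that is related to the change in outcome, with a rate or mechanism that differs by arm. The stronger reading, that different dropout rates by themselves bias the result, fails: 35% versus 15% unrelated to outcome gives zero.

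If that condition is met, the illustrative bias is about 0.01 to 0.05 baseline SD under a shared mechanism at 30% versus 20% loss. Under a strong one-arm mechanism it is about 0.04 to 0.16, with the upper end at roughly 0.10 to 0.16. The detectable difference is about 0.2 to 0.33. These sizes rest on assumed arm-specific loss, slopes and 6-week correlations. Only the 75%, the range of ρ and the range of ICC come from the plan.

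**What to change.** In section 5.6:

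- Limit the retention sentence to participants who do not complete all sessions but are assessed.
- Make the primary 6-month analysis one that adjusts for the baseline score and uses the 6-week score under missing at random. Two suitable forms are cohort-aware multiple imputation by arm before the GEE, or a joint model of the 6-week and 6-month scores with baseline as covariate and cohort clustering.
- State how deaths are handled, without imputing scores after death. Death is an anticipated event in the plan (6.1 Adverse Events).
- Report retention by arm at 6 weeks and 6 months.
- Add one delta-shift sensitivity analysis for loss that is not at random.

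The cost is SAP wording, a little more analysis work and reliance on a missing-at-random assumption, which the delta-shift analysis tests. All the scores needed are already scheduled in Table 2.
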